8.1 Subject numbering

Subjects will be assigned an 8 digits subject ID number consisting of a four digits site number (2520) and a 4 digits subject ID starting with 1xxx. Subject numbering will be assigned sequentially as subjects are recruited/screened (e.g., 1001, 1002, and 1003, etc.). The first subject enrolled will have a subject ID of 2520-1001.

8.2. Ethical considerations

The study will be conducted in accordance with applicable regulatory requirements, the International Conference on Harmonisation (ICH) E6 Guideline for Good Clinical Practice (GCP), the Declaration of Helsinki, any other applicable regulatory requirements, and Institutional Review Board (IRB) or Independent Ethics Committee (IEC) requirements.

9. SCHEDULE OF EVENTS

ASSESSMENTS	Screening		Treatment											ONLY If EOT = Day 14 ^{2,4}	ONLY If EOT = Day 14 ^{2,4}	Continued Treatment visits for eligible subjects (CTV)	Follow-up			
	Up to 72 hrs prior to Day 1	Day 1 (ba seli ne)	Day 2	Day 3	Day 4	Day 5	Day 6	Day 7	Day 8	Day 9	Day 10	Day 11	Day 12	Day 13	Day 14 ⁴	Day 21 (+/- 2 days)	Day 28 (+/- 4 days)	Dosing Q 3 wks +/- 2 days: Week 5, 8,	Week 12 for all subjects	4 weeks (+/- 7 Days) after last Pamrevlu mab dose
Informed consent	Х																			
Eligibility criteria	Х																			
Medical History	Х																			
Demographic information	Х																			
Physical examination	Х																			
Vital signs ³	Х	X1	Х	Х	Х	Х	Х	X ¹	Х	Х	Х	Х	Х	Х	X ¹			X ¹		
ECG	Х																			
Chest HRCT	Х														Х				Х	
Laboratory assessments (local)	Х	Х	Х	Х	Х	Х	Х	Х	Х	Х	Х	Х	Х	Х	Х			Х		
Blood samples for Immunogenicity Assessments		Х						Х							Х					Х
Urine pregnancy test ⁶	Х																			
Randomization		Х																		
Concomitant medications	Х	Х	Х	Х	Х	Х	Х	Х	Х	Х	Х	Х	Х	Х	Χ	Х	Х	X	Х	Х
Infusion		Х						Х							Х					
Arterial Blood Gases (ABG) ³	Х	Х	Х	Х	Х	Х	Х	Х	Х	Х	Х	Х	Х	Х	Х					
PaO ₂ /FiO ₂ ³	Х	Х	Х	Х	Х	Х	Х	Х	Х	Х	Х	Х	Х	Х	Χ					
Resting SpO ₂ (3 times/day) ³	Х	Х	Х	Х	Х	Х	Х	Х	Х	Х	Х	Х	Х	Х	Х					
Oxygen supplementation Needs ^{3, 5}	Х	Х	Х	Х	Х	Х	Х	Х	Х	Х	Х	Х	Х	Х	Х					
Adverse events	Х	Х	Х	Х	Х	Х	Х	Х	Х	Х	Х	Х	Х	Х	Х	Х	Х	Х	Х	Х
Survival and Hospital Discharge Status																Х	Х		Х	Х

¹On infusion days, vitals taken within 30 minutes prior and 30 min after infusion; otherwise vitals taken daily ²Follow-up visits to be done in person or by phone ³Only measured until subject is discharged from the ICU/CCU. ⁴Subjects ending treatment on Day 14 should be contact by phone or return for a visit on Days 21 and 28 for a vital status check. ⁵Including need for mechanical ventilation including ventilator settings, or supplemental oxygen including mode of oxygen delivery ⁵Only for women of childbearing potential or last menstruation <1 year.

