3.4. Safety endpoints

Safety endpoints will be:

- 1.3.4.1. Treatment-emergent adverse events and serious adverse events.
- 1.3.4.2. Treatment-emergent adverse events leading to premature discontinuation of study treatment.
- 1.3.4.3. Hypersensitivity reactions including anaphylactic/anaphylactoid reactions.
- 1.3.4.4. Treatment-emergent laboratory abnormalities
- 1.3.4.5. Assessment of immunogenicity.

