4. STUDY DESIGN AND METHODS

4.1. Study design

This is a randomized, open-label, parallel-arm study to investigate the efficacy and safety of pamrevlumab in patients with documented SARS-CoV-2 infection. The study consists of screening, a treatment period, and a follow-up period.

The study will enroll patients who have been hospitalized and who are not currently on invasive mechanical ventilation. The treatment period is open ended, and patients will be randomized to treatment with pamrevlumab or standard of care in a 1:1 ratio according to a pre-generated randomization list. Pamrevlumab dosing, 30 mg/kg IV, will be administered at day 1, day 7 and day 14. Day 1 is defined as the day of randomization which must also include administration of the first dose of pamrevlumab for patients in the active treatment arm.

Based on Investigator's decision, treatment may be continued every 3 weeks after day 14, up to 11 weeks.

Since the treatment scheme of pamrevlumab for this study is more intense as compared to previous studies conducted in IPF patients, as a further safety measure the first 3 patients randomized to receive the experimental drug will be treated one at a time, leaving a 1-week observation period between them.

A follow-up by visit or phone call will be performed 8 and 12 weeks after the end of the last dose of treatment. The treatment period for an individual patient will not exceed 11 weeks. The end of the study is defined as last patient last follow-up visit/phone call.

The study design has a total sample size of approximately 68 patients and consists of two stages. At the end of Stage 1 (Stage 1 requires 23 patients on pamrevlumab treatment arm), analyses of efficacy and safety will take place with a potential to stop the study for futility or for efficacy. A data

review committee composed of experts in respiratory medicine and intensive care will be involved in study oversight and interpretation of the study results. In patients showing worsening of clinical condition, independently of the treatment arm, the Investigator is free to introduce any therapy considered necessary.

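### Scheduled laboratory sampling ends on the day of the third infusion for patients who stop at Day 14 and, by inference, for all controls; only continuing pamrevlumab patients have later draws.

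*Protocol*

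**What the plan says.** Protocol section 3.4 names "Treatment-emergent laboratory abnormalities" among the safety endpoints, and safety and tolerability are the only secondary objective (section 2.2).

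On dosing, section 4.1 states: "Pamrevlumab dosing, 30 mg/kg IV, will be administered at day 1, day 7 and day 14". At the investigator's discretion, "treatment may be continued every 3 weeks after day 14, up to 11 weeks".

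In section 9, the row that begins "Laboratory assessments (local" carries marks at screening, on each of Days 1 to 14, and in the column whose heading begins "Continued Treatment visits for eligible subjects (CTV". It is blank at Day 21, Day 28, Week 12 and the visit 4 weeks after the last pamrevlumab dose. A footnote to the table says that patients ending treatment on Day 14 "should be contact by phone or return for a visit on Days 21 and 28 for a vital status check".

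The row "Blood samples for Immunogenicity Assessments" does have a late mark, at 4 weeks after the last dose. Adverse events and concomitant medications are recorded in every later column.

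**The concern.** The last scheduled laboratory day for a patient who stops at Day 14 is the day the third dose is given. Any laboratory effect that appears on a later day is seen only if someone happens to order a test. Adverse event questioning, possibly by phone, cannot reliably pick up a silent change such as a rise in a liver enzyme or a fall in a cell count.

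The late draws that do exist are tied to dosing visits. They therefore come only from pamrevlumab patients whom the investigator chose to keep on treatment. In a population with an evolving acute illness, late abnormalities in that group cannot be set against controls sampled at the same time.

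An analysis plan cannot repair this, because it cannot analyse samples that were never scheduled. Section 4.1 itself calls the regimen more intense than earlier use in IPF and adds a safety measure for that reason: one week between the first three treated patients. That measure does not extend laboratory follow-up beyond Day 14.

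**Working it through.** **Step 1. Is the table read correctly?** The schedule has 20 columns: screening, Days 1 to 14, Day 21, Day 28, continued treatment, Week 12, and 4 weeks after the last dose. The rows for laboratory tests, vital signs, infusion, immunogenicity, HRCT, adverse events and survival status all resolve to these 20 columns. The adverse event row is filled in all 20. The blanks in the laboratory row are therefore real and not a product of reading the PDF.

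**Step 2. Count the scheduled laboratory occasions.**

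| Group | Screening to Day 14 | After Day 14 |
|---|---|---|
| Pamrevlumab, stops at Day 14 | 1 + 14 = 15 | 0 |
| Control (inferred) | 15 | 0 |
| Pamrevlumab, continues | 15 | 2 (Weeks 5, 8), or 3 with Week 11 |

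Two entries are inferences. Controls are given no continued-treatment draws because that column is a dosing visit; the protocol does not state which later columns apply to them. Week 11 follows from the 11-week limit in section 4.1 (2 + 3 + 3 + 3 = 11), whereas the visible column heading breaks off after Week 8. Counting Days 2 to 14 as post-baseline gives 13 occasions for the first two groups and 15 or 16 for the third.

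**Step 3. How much exposure falls after the last draw?** No half-life is given, so this is an illustration. Take a linear one-compartment model with equal doses on Days 1, 7 and 14, half-life h and k = ln 2 / h. In units of the first peak:

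- Peak after dose 2: P2 = 1 + e^(-6k)
- Peak after dose 3: P3 = 1 + e^(-7k) + e^(-13k)
- Share of total three-dose AUC that falls after the Day 14 dose: P3 / 3

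| Assumed h (days) | P2 | P3 | P3/P2 | AUC share after Day 14 |
|---|---|---|---|---|
| 3 | 1.25 | 1.25 | 1.00 | 42% |
| 5 | 1.44 | 1.54 | 1.08 | 51% |
| 7 | 1.55 | 1.78 | 1.14 | 59% |
| 14 | 1.74 | 2.23 | 1.28 | 74% |
| 21 | 1.82 | 2.44 | 1.34 | 81% |

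At h = 21, for example: e^(-7k) = 2^(-7/21) = 0.794 and e^(-13k) = 2^(-13/21) = 0.651, so P3 = 2.44 and P3/3 = 0.81. The AUC runs to infinite time.

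**Step 4. What would a later draw see?** The concentration as a share of the peak after dose 3 is 2^(-t/h), with t in days after Day 14. For h from 3 to 21 days:

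- Day 21 (t = 7): 20% to 79%
- Day 28 (t = 14): 4% to 63%
- 4 weeks after the dose (t = 28): 0.2% to 40%

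**The case against.** A reader might infer three stronger statements. The protocol supports none of them.

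*Peak exposure is never sampled.* Daily draws on Days 8 to 13 follow the second dose, and on the figures above the third peak is only about 1.0 to 1.34 times the second. The protocol also does not say whether the Day 14 sample is taken before or after the infusion.

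*The between-arm comparison is biased.* That presumes a table of any post-baseline abnormality, which the protocol does not specify. Windowing of laboratory data is normally left to the SAP, which is not available here. What stands is that post-Day-14 values exist in one arm only.

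*Late laboratory effects cannot be detected.* Adverse events are still recorded at every later contact, patients still in hospital receive usual care, and section 8 sends laboratory reports to the database. What is missing is systematic sampling, not all detection.

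The urgency is also tempered by section 1.6, which reports no safety concerns in pancreatic cancer with 35 mg/kg on days 1, 7 and 14 and longer continuation. That is reassuring, but it does not supply laboratory data in COVID-19 patients.

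A fair objection to the remedy is that a panel 4 weeks after the last dose comes late (0.2% to 40% of the third peak) and, being anchored to a pamrevlumab dose, adds another draw in one arm only. This stands. It is why the fix also uses Week 12 and, where possible, Days 21 and 28.

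**Conclusion.** The gap is real but bounded. Patients who stop at Day 14 have no scheduled safety panel after the day of the third dose, and laboratory values after Day 14 have no concurrent control. The number of late draws is 0 against 2 or 3.

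The first statement rests on the schedule itself. The second also rests on the inference that controls have no continued-treatment visits. The exposure share of 42% to 81% depends wholly on the assumed half-life and shows only that a substantial part of exposure lies beyond the last draw. No claim is made that the peak is missed, that a planned comparison is biased, or that the endpoint cannot be assessed at all. Daily sampling to Day 14 remains a strength of the plan. This is a cheap improvement to the safety data, not a flaw that undermines the trial.

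**What to change.** 1. Reconcile the post-treatment contacts. Section 9 has a visit 4 weeks after the last dose with an immunogenicity sample, section 7 puts the last immunogenicity sample 12 weeks after the end of treatment, and section 4.1 puts follow-up by visit or phone at 8 and 12 weeks after the last dose.
2. Add the local laboratory panel to the post-treatment immunogenicity draw, at whatever time that reconciliation settles. This covers pamrevlumab patients only.
3. Add the panel to the Week 12 visit for all subjects, where HRCT already requires attendance. This gives both arms a common late value.
4. Where the Day 21 or Day 28 contact is in person, take the panel then in both arms. State which later columns apply to controls, since those two columns are headed by the end of treatment at Day 14. These draws will come selectively from patients who are seen in person, so report how many were taken in each arm.
5. State whether the Day 14 sample is taken before or after the infusion.
6. Compare arms on draws scheduled in both arms, and list the continued-treatment values separately as pamrevlumab-only data.

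The cost is one or two routine local panels per patient, largely at visits where blood is drawn or attendance is already required, plus schedule wording.

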4.7. Statistical methods

For futility testing in Stage 1, a responder rate definition will be used. Patients randomized to receive pamrevlumab are considered responders if the total number of days on ventilation is \leq 15 days after the first dose of pamrevlumab. In addition, chest HRCT scans obtained at enrollment and day 14 \pm 2 will used as supportive analyses in the assessment of futility.

Analysis of continuous endpoints will be conducted using analysis of covariance (ANCOVA) model with baseline value as a covariate and relevant baseline prognostic factors as other covariates.

Analysis of categorical endpoints will be conducted using either Fishers Exact test or Cochran-Mantel-Haenszel test comparing the categories between the two treatment arms.

Analysis of the time to mechanical ventilation, time to all-cause mortality, and time to hospital discharge, respectively, will be undertaken by plotting Kaplan-Meier curves. Hazard ratios will be estimated using the Cox proportional hazards model and these will be presented together with 95% two-sided confidence intervals. Other statistical methods will be applied, as appropriate.

5. Subject withdrawal criteria

Subjects may withdraw from the study at any time, for any reason. Reasons for discontinuing study drug treatment, as well as reasons for withdrawing from study, will be captured on CRF.

Reasons for withdrawing the subject from the study may include the following:

- 5.1. Any safety concern in the Investigator's opinion, that precludes further study participation
- 5.2. Pregnancy
- 5.3. Withdrawal of Consent

6. Pamrevlumab: storage, preparation and use

Pamrevlumab is a fully human IgG1 kappa monoclonal antibody that binds to CTGF and is formulated as solution for administration by IV infusion.

Pamrevlumab is supplied in single-use glass vials containing sterile, preservative-free solution 10 mg/ml pamrevlumab. The solution is composed of 10 mg/mL pamrevlumab, 1.60 mg/mL L-histidine, 3.08 mg/mL L-histidine HCl, 8.01 mg/mL sodium chloride, and 0.05 mg/mL polysorbate 20, resulting in a solution with a tonicity of approximately 290 mmol/kg and a pH of 6.0.

Vials of pamrevlumab must be stored refrigerated (2°C to 8°C), in a temperature- controlled and monitored environment, protected from light, and in a securely locked area to which access is limited to appropriate study personnel. Documentation of the storage conditions must be maintained.

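### The pregnancy test is scheduled once, at screening, although optional pamrevlumab dosing can run to Week 11, up to about 79 days later

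*Protocol*

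**What the plan says.** The schedule of events in Protocol section 9 has a separate row for the "Urine pregnancy test". It carries one mark, in the screening column, whose window is "Up to 72 hrs prior to Day 1". A footnote limits the test to women who could be pregnant. The row is blank on Days 1, 7 and 14, at the continued-treatment visits and at follow-up.

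On dosing, section 4.1 states: "Pamrevlumab dosing, 30 mg/kg IV, will be administered at day 1, day 7 and day 14". The investigator may then extend: "treatment may be continued every 3 weeks after day 14, up to 11 weeks". The same section caps exposure: "The treatment period for an individual patient will not exceed 11 weeks". The matching column of the schedule is headed "Dosing Q 3 wks +/- 2 days: Week 5, 8"; the heading breaks off there in the text available.

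Pregnancy appears in two other places. Section 4.3 lists it as an exclusion. Section 5 lists it as "5.2. Pregnancy" under the introduction "Reasons for withdrawing the subject from the study may include the following".

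**The concern.** The protocol treats pregnancy as a reason not to enter and as a possible reason to stop, but it looks for it only before entry. A woman who tests negative at screening and becomes pregnant afterwards could receive up to three further infusions of an investigational antibody before anyone knows. The investigator's discretion to withdraw her is of use only if the pregnancy has been detected.

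The stake is patient safety alone. The protocol describes no specific fetal risk from pamrevlumab, and the primary endpoint, the two-stage decision rule and the sample size are unaffected.

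**Working it through.** **Inputs**
- Earliest screening test: 72 hours, that is 3 days, before Day 1 (section 9).
- Fixed doses: Days 1, 7 and 14 (section 4.1).
- Optional doses: every 21 days after Day 14, to a limit of 11 weeks (section 4.1), with a visit window of ±2 days (section 9).

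**Step 1: optional dosing days**, Day 14 + 21k
- k = 1: 14 + 21 = Day 35 (Week 5)
- k = 2: 14 + 42 = Day 56 (Week 8)
- k = 3: 14 + 63 = Day 77 (Week 11)
- k = 4: 14 + 84 = Day 98 (Week 14), beyond the limit

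Weeks 5 and 8 agree with the legible part of the schedule heading. Day 77 agrees with the protocol's own limit of 11 weeks. The maximum is therefore three optional infusions.

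**Step 2: interval from test to dose**, (dose day − 1) + days from test to Day 1

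| Dose | Test on Day 1 (lead 0) | Test 3 days earlier |
|---|---|---|
| Day 14 | 14 − 1 = 13 | 13 + 3 = 16 |
| Day 35 | 35 − 1 = 34 | 34 + 3 = 37 |
| Day 56 | 56 − 1 = 55 | 55 + 3 = 58 |
| Day 77 | 77 − 1 = 76 | 76 + 3 = 79 |

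The ±2-day window widens the Day 77 range of 76–79 days to 74–81. The upper edge would put the dose on Day 79, past the 11-week cap, so 79 days is the longest interval if the cap is respected.

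**Step 3: is pregnancy looked for elsewhere after screening?** The continued-treatment column has marks for vital signs, local laboratory assessments, concomitant medications and adverse events. The content of the laboratory panel is not stated, and the pregnancy test has its own row, so the panel cannot be counted as a test. The safety section (7) covers adverse-event recording, hypersensitivity monitoring and immunogenicity sampling; it does not mention pregnancy testing.

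**Step 4: interval after the fix.** With a test before each optional infusion, the longest scheduled interval from test to dose is the one to Day 14: (14 − 1) + 3 = 16 days.

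**Step 5: scale, on assumed shares.** The protocol gives neither the share of women of childbearing potential nor the share who continue after Day 14. Assume 5–15% and 25–50%:
- 34 pamrevlumab patients (both stages): 34 × 0.05 × 0.25 = 0.4 to 34 × 0.15 × 0.50 = 2.6 women
- 23 pamrevlumab patients (Stage 1 only): 23 × 0.05 × 0.25 = 0.3 to 23 × 0.15 × 0.50 = 1.7 women

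These are women who would be tested. Pregnancies would be a fraction of that.

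**The case against.** The strongest reply is that nothing in the protocol is misstated. The exclusion is served by the screening test. The withdrawal list is permissive, and its other entries, such as any safety concern, have no scheduled test either. How often to repeat a pregnancy test is a monitoring choice. Continued dosing is optional, decided by the investigator, and accompanied by laboratory and adverse-event review. Patients enter hospitalised, on supplemental oxygen and aged 18 to 80, so conception within 11 weeks is likely to be rare.

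Much of this stands. There is no contradiction in the text, the number of women is small, and the harm is unquantified. The grid is also imperfect: the continued-treatment column is headed as dosing yet has no mark in the infusion row, so a blank cell there is weaker evidence than usual. A site could also test on its own initiative.

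It does not close the gap. The other marks in that column are present, and no other text shown supplies a test. A site that follows the schedule exactly would re-dose weeks later without the check required of the same women, for the same drug, at entry. The permissive withdrawal wording does not help, because that discretion cannot be used on a pregnancy nobody has found. If only the legible Weeks 5 and 8 are accepted, the intervals are still 37 and 58 days.

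**Conclusion.** The concern holds. The only scheduled pregnancy test can precede the optional infusions by 37, 58 and 79 days, and nothing in the protocol requires detection in between. The intervals follow from the protocol's own dates, taking the earliest permitted screening test and the nominal dosing days; they need no outside assumption. The head count of roughly 0.3 to 2.6 women does rest on assumed shares and is given for scale only.

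This is a low-cost safety improvement that should be made. It has no bearing on the trial's statistical properties.

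**What to change.** In the section 9 schedule, mark the existing urine pregnancy test, for the women its footnote already names, before each continued-treatment infusion (about Weeks 5, 8 and 11), with the result available before dosing.

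A mark at the follow-up visit 4 weeks after the last dose is a useful addition when that visit is in person; follow-up may otherwise be by phone. It would identify a pregnancy exposed to the drug but would not prevent exposure, so it is secondary.

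The cost is one changed row and up to three urine strips per continuing woman, or four with the follow-up test. No visit is added, because these patients already attend for infusion, vital signs and laboratory samples.
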